### 6.3.9 Day 112 (±10 days)

Patients will undergo the following procedures on the Day 112 study visit:

- Collect blood samples for the following tests:
  - Serum TTR protein, vitamin A, and RBP. Additionally, aliquots of serum samples will be taken and frozen, to permit testing of additional proteins related to ATTR.
  - o Day 112 PK sample.
- Collect urine for PK analysis.

#### 6.3.10 Day 208 (±2 weeks)

Patients will undergo the following procedures on the Day 208 study visit:

- Collect blood samples for the following tests:
  - Serum TTR protein, vitamin A, and RBP. Additionally, aliquots of serum samples will be taken and frozen, to permit testing of additional proteins related to ATTR.
  - o Anti-PEG antibodies (IgG and IgM).
  - o Day 208 PK sample.
- Collect urine for PK analysis.

#### 6.4 Early Termination

Patients coming off study before Day 56 will return to the study site to complete their Early Termination visit which will include Day 56 assessments. Patients coming off study after Day 56 and before Day 208 will return to the study site to complete their Early Termination visit which will include Day 208 assessments.

#### 6.5 Unscheduled Visits

Unscheduled visits may occur if deemed clinically significant by the Investigator.

A patient will be followed every 2 weeks ( $\pm 3$  days) after Day 56 if their TTR level continues to recover, but is not found to have returned to within at least 80% of the baseline value. The patient will have blood samples collected for the following clinical laboratory tests at these visits:

 Serum TTR protein, vitamin A, and RBP. Additionally, aliquots of serum samples will be taken and frozen, to permit testing of additional proteins related to ATTR.

These patients will be followed and discussed at each SRC meeting until their TTR level returns to within at least 80% of the baseline value.

# 6.6 Participation in an Open-label Extension Study

An open-label extension study at the recommended Phase 3 dose and regimen (as derived from Study ALN-TTR02-002) is planned, which will enable the patients who enrolled in Study ALN-TTR02-002 to receive additional, long-term dosing and safety follow-up. For some of the patients, this may preclude the completion of all of the follow-up period assessments of Study ALN-TTR02-002 if they are deemed eligible to participate in the extension study prior to completion of the full follow up through Day 208. Such patients will be followed up for a minimum of 28 days after their last dose in the current ALN-TTR02-002 study prior to being enrolled in the extension study. The extension study will be implemented only after dose escalation is completed in Study ALN-TTR02-002, with post second dose follow-up through Day 208 in at least 1 cohort at the highest dose deemed safe.

#### 7 STUDY ASSESSMENTS

### 7.1 Demographic Data and Medical History

Patient demographic data will be obtained during screening, and a complete medical history will be obtained during screening and updated on Days 0 and 28 (or Days 0 and 21 for optional cohorts dosed once every 3 weeks) as needed. The medical history is to include background information confirming a diagnosis of ATTR through biopsy and ongoing documented signs/symptoms of the disease (e.g., sensory, motor, or autonomic neuropathy) that are at least mild to moderate in severity.

### 7.2 Safety Assessments

All safety assessment measures will be recorded in the patient's CRF.

### 7.2.1 Physical Examination

Physical examinations will be performed by a physician and will include the examination of the following: general appearance, head, eyes, ears, nose, throat, chest/respiratory, heart/cardiovascular, gastrointestinal/liver, musculoskeletal/extremities, dermatological/skin, thyroid/neck, lymph nodes, and neurological/psychiatric.

Body weight will be measured at Screening for assessment of eligibility, and on the Day 0 and 28 (or Days 0 and 21 for optional cohorts dosed once every 3 weeks) study visits. The weight measured pre-dose on Days 0 and 28 will be used to calculate the first and second dose of ALN-TTR02, respectively.

Height will be measured at Screening.

#### 7.2.2 Vital Signs

Vital signs are to be measured at Screening and the Day 2, 14, 30, 42, and 56 (or Days 2, 14, 23, 35, and 56 for optional cohorts dosed once every 3 weeks; or time of early termination, if applicable) study visits and include systolic/diastolic blood pressure, pulse rate, respiration rate, and oral body temperature. Vital signs will be measured in the supine position using an automated instrument after the patient has rested comfortably for 10 minutes. Each patient's blood pressure should be taken using the same arm. Oral temperature will be recorded in Celsius. Heart rate will be counted for a full minute and recorded in beats per minute. Respirations will be counted for a full minute and recorded in breaths per minute.

On Days 0 and 28 (or Days 0 and 21 for optional cohorts dosed once every 3 weeks), serial vital signs are to be measured within 30 minutes pre-dose, at EOI; and at 30 (±5) minutes; 1, 2, and 3 (±15 minutes) hours; 6, 12, and 18 hours (±30 minutes) post-infusion. On Days 1 and 29 (or Days 1 and 22 for optional cohorts dosed once every 3 weeks), serial vital signs are to be measured at 24 hours (+30 minutes) post-infusion.

For the safety of the patient, additional vital signs may be added at the discretion of the Investigator.

# 7.2.3 Echocardiogram

An echocardiogram is to be conducted during Screening, to assess any cardiac abnormalities as part of the screening criteria. If a normal echocardiogram has been obtained within the past 90 days, there is no need to perform an echocardiogram at Screening.

### 7.2.4 Electrocardiogram

Computerised 12-lead ECG recordings will be obtained. Each lead shall be recorded for at least 3 beats at a speed of 25 mm/s. Triplicate recordings will be made at the time points indicated in Table 1-1.

Serial ECGs will be collected in triplicate 30 minutes prior to dosing (Days 0 and 28 [or Days 0 and 21 for optional cohorts dosed once every 3 weeks]), EOI, and 30 (±5) minutes, 2 and 4 (±15 minutes) hours, and on Days 1 and 29 (or Days 1 and 22 for optional cohorts dosed once every 3 weeks) at 24 (+30 minutes) hours post-infusion.

The following electrophysiologic parameters will be assessed: rhythm, ventricular rate, PR interval, QRS duration, and QT interval. Either Bazett's and/or Fridericia's formula will be used to calculate the heart rate corrected QT interval (QTc).

The Investigator or designee is responsible for reviewing the ECG to assess whether the ECG is within normal limits and to determine the clinical significance of the results. Prior to discharge from the hospital on Days 1 and 29 (or Days 1 and 22 for optional cohorts dosed once every 3 weeks), the ECG must be reviewed by the Investigator and the results deemed not clinically significant. Any clinically significant findings must be discussed with the medical monitor to determine whether patient can be discharged and to formulate plans for patient follow-up.

For any clinically significant abnormal results, the Investigator must contact the Medical Monitor to discuss continued participation of the patient in the study (e.g., ischemic ECG changes, wave/interval changes, or arrhythmia).

### 7.2.5 Pulse Oximetry

Arterial oxygen saturation will be assessed by serial pulse oximetry on Days 0 and 28 (or Days 0 and 21 for optional cohorts dosed once every 3 weeks) within 30 (±5) minutes pre-dose; at EOI; at 30 (±5) minutes; at 1, 2, 3 hours (±15 minutes); and at 6, 12, and 18 hours (±15 minutes) post-infusion on Days 0 and 28 (or Days 0 and 21 for optional cohorts dosed once every 3 weeks); and at 24 hours (+30 minutes) post-infusion on Days 1 and 29 (or Days 1 and 22 for optional cohorts dosed once every 3 weeks).

# 7.2.6 Cardiac Monitoring

Continuous cardiac monitoring will be performed via telemetry starting no later than 30 minutes prior to dosing and continuing through 24 hours (+1 hour) post-dose.

# 7.2.7 Clinical Laboratory Tests

Laboratory tests of hematology, serum chemistries, liver function, coagulation studies, CRP, urinalysis, pregnancy (serum and urine), hepatitis B and C serologies, lipids, and thyroid function will be performed by each study center's local laboratory.

The following laboratory tests will be performed at the laboratories listed below:

Cytokines, complement factor Bb, anti-PEG antibody formatio
 Tryptase

Additional laboratory tests may be performed centrally, depending upon the capabilities of the local laboratory.

Prior to study drug administration, samples for clinical laboratory tests are to be collected and results of serum chemistries, hematology, LFTs, and coagulation parameters (where applicable) reviewed and approved by the Investigator or qualified designee (e.g., physician's assistant, nurse practitioner).

In the event of an unexplained clinically relevant abnormal laboratory test occurring after study drug administration, the test should be repeated and followed up at the discretion of

the Investigator until it has returned to the normal range or stabilized, and/or a diagnosis is made to adequately explain the abnormality.

The following clinical laboratory parameters are to be determined:

Hematology	
Hematocrit	• Neutrophils, absolute and %
• Hemoglobin	• Lymphocytes, absolute and %
• Red blood cell (RBC) count	
 
Monocytes, absolute and %
 

• White blood cell (WBC) count	• Eosinophils, absolute and %
Mean corpuscular volume	• Basophils, absolute and %
Mean corpuscular hemoglobin	• Platelet count
Mean corpuscular hemoglobin concentration	
Serum Chemistries a	
• Sodium	• Glucose
• Potassium	• Phosphate
• Blood urea nitrogen (BUN)	• Lactate dehydrogenase (LDH)
• Creatinine	• Troponin I
• C-reactive protein (CRP)	• Creatinine phosphokinase (CPK)
• Albumin	• Myocardial band enzymes of CPK
• Calcium	(CPK-MB)
Liver Function Tests	
• Aspartate transaminase (AST)	Alkaline phosphatase
Alanine transaminase (ALT)	Bilirubin (total and direct)
Thyroid Function Tests	
Thyroid stimulating hormone (TSH)	Triiodothyronine (T3)
• Thyroxine (T4)	
Coagulation Studies	
Prothrombin time (PT)	International normalized ratio (INR)

 
Activated partial thromboplastin time (aPTT)
 
	

Se	rol	nσ	v
SC	נט ו	υŁ	٧

- Anti-PEG antibody formation (IgG and IgM) Hepatitis C (anti-HCV Ab)
- Hepatitis B (HBsAg and HBsAb)

#### Urinalysis

- Visual inspection for color and appearance
- pH
- Specific gravity
- Ketones
- Protein
- Glucose

- Leukocytes
- Bilirubin
- Nitrite
- Urobilinogen
- Microscopic inspection of sediment

### **Complement Factors**

Bb

C3ab

### **Cytokines**

- Interferon-alpha (IFN-α)
- Interferon-gamma (IFN-γ)
- Tumor necrosis factor-alpha (TNF- $\alpha$ )
- Interleukin-1β (IL-1β)
- IL-1 receptor antagonist (IL-1 RA)

- Interleukin-6 (IL-6)
- Interleukin-12 (IL-12)
- Interferon-inducible protein-10 (IP-10)
- Granulocyte-colony stimulating factor (G-CSF)

### Other

- β-human chorionic gonadotropin (women of child-bearing potential only)
- Tryptaseb
- A non-fasting lipid panel (including total cholesterol, high density lipoprotein [HDL], low density lipoprotein [LDL], very low density lipoprotein [VLDL], and triglycerides) will be performed pre-dose on Day 0 only.
- b To be performed only in the event of an infusion reaction.

Additional and repeat testing may be performed at the discretion of the Investigator.

### 7.2.7.1 Hematology, Serum Chemistries, and Urinalysis

Blood samples for hematology and serum chemistries and urine for urinalysis are to be collected at Screening, pre-dose on Day 0 (unless the screening evaluations were performed within the previous 72 hours) and Day 28 (or Day 21 for optional cohorts dosed once every 3 weeks), and on the Day 1, 14, 29, 42, and 56 study visits (or Days 1, 14, 22, 35, and 56 for optional cohorts dosed once every 3 weeks), or at the time of early termination, if applicable.

Prior to discharge from the hospital on Days 1 and 29 (or Days 1 and 22 for optional cohorts dosed once every 3 weeks), local serum laboratories (specifically, sodium, potassium, creatinine, albumin, calcium, glucose, and phosphate) must be reviewed by the Investigator and the results deemed not clinically significant. Any clinically significant findings must be discussed with the medical monitor to determine whether patient can be discharged and to formulate plans for patient follow-up.

Blood for CRP is to be collected pre-dose (within 10 minutes) on Days 0 and 28 (or Days 0 and 21 for optional cohorts dosed once every 3 weeks), and at 2 and 6 hours ( $\pm 15$  minutes), and 24 hours ( $\pm 120$  minutes) post-infusion.

#### 7.2.7.2 Liver Function Tests

Blood for LFTs is to be collected at Screening, pre-dose on Day 0 (unless the screening evaluations were performed within the previous 72 hours) and Day 28, and at the Day 1, 2, 7, 14, 29, 30, 35, 42, and 56 study visits (or Days 1, 2, 7, 14, 22, 23, 28, 35, and 56 for optional cohorts dosed once every 3 weeks), or at the time of early termination, if applicable. These samples are to be processed at the site's local laboratory.

Prior to discharge from the hospital on Days 1 and 29 (or Days 1 and 22 for optional cohorts dosed once every 3 weeks), local LFTs must be reviewed by the Investigator and the results deemed not clinically significant. Any clinically significant findings must be discussed with the medical monitor to determine whether patient can be discharged and to formulate plans for patient follow-up.

### **7.2.7.3 Lipid Panel**

Blood for determination of the lipid panel is to be collected pre-dose on Day 0.

### 7.2.7.4 Coagulation Studies

Blood for coagulation studies is to be collected at Screening, pre-dose on Days 0 (unless the screening evaluations were performed within the previous 72 hours) and 28 (or Day 21 for optional cohorts dosed once every 3 weeks), at the Days 1 and 29 (or Days 1 and 22 for optional cohorts dosed once every 3 weeks) study visits.

### 7.2.7.5 Thyroid Function Tests

Blood for thyroid function tests is to be collected at Screening, pre-dose on Days 0 (unless the screening evaluations were performed within the previous 72 hours) and 28 (or Days 0 and 21 for optional cohorts dosed once every 3 weeks), and at Day 14, 42, and 56 (or Days 14, 35, and 56 for optional cohorts dosed once every 3 weeks) study visits, or

at the time of early termination, if applicable. These samples are to be processed at the site's local laboratory.

### **7.2.7.6** Complement

Blood for complement factor Bb, is to be collected pre-dose (within 10 minutes) on Days 0 and 28 (or Days 0 and 21 for optional cohorts dosed once every 3 weeks), and 30 ( $\pm$  5) minutes and 2 ( $\pm$  15 minutes) and 24 hours ( $\pm$  120 minutes) post-infusion. If the patient experiences an infusion reaction, a blood sample for analysis of complement factors (including complement C3a) should be obtained within 1 hour of the start of the reaction.

### **7.2.7.7 Cytokines**

Blood for cytokine assessment is to be collected pre-dose (within 10 minutes) on Days 0 and 28 (or Days 0 and 21 for optional cohorts dosed once every 3 weeks), at 2 ( $\pm$ 15 minutes), and 6 hours ( $\pm$ 15 minutes), and 24 hours ( $\pm$ 120 minutes) post-infusion. If the patient experiences an infusion reaction, a blood sample for analysis of cytokines should be obtained within 1 hour of the start of the reaction.

## 7.2.7.8 Pregnancy Test

A serum pregnancy test will be performed for women of child-bearing potential at Screening, at the Day 56 study visit, and any time pregnancy is suspected. A urine pregnancy test will be performed pre-dose on Day 0 for women of child-bearing potential, the results of which must be known prior to administration of study drug. Patients who are pregnant are not eligible for study participation. Patients determined to be pregnant while on study will be followed until pregnancy outcome is known (see Section 8.12).

### 7.2.7.9 Hepatitis B/C Status

Blood for HBV (Hepatitis B surface antibody [HbsAb], Hepatitis B surface antigen [HbsAg]), and HCV (anti-HCV) are to be collected at Screening. Patients with positive HBV or HCV serologies are not eligible for study participation.

# 7.3 Pharmacodynamic Assessments

# 7.3.1 Transthyretin Protein

Blood for serum TTR protein levels (WT and mutant) is to be collected at Screening, immediately prior (within 10 minutes) to the administration of the premedications, immediately pre-dose (within 10 minutes) on Days 0 (Baseline) and 28, and on Days 1, 2,

7, 10, 14, 21, 29, 30, 35, 38, 42, 49, 56 (end-of-study), 112, and 208 or at the time of early termination. For optional cohorts dosed once every 3 weeks, blood for serum TTR protein levels will be collected at Screening, immediately prior (within 10 minutes) to the administration of the premedications, immediately pre-dose (within 10 minutes) on Days 0 (Baseline) and 21, and on Days 1, 2, 7, 10, 14, 22, 23, 28, 31, 35, 42, 49, 56 (end-of-study), 112, and 208 or at the time of early termination. A patient will be followed every 2 weeks after Day 56 if the TTR level continues to recover but is not found to have returned to within at least 80% of the baseline value. If this occurs, the patient will be followed and discussed at each SRC meeting until the TTR level returns to within at least 80% of the baseline value. Additionally, aliquots of serum samples drawn for measurement of TTR levels will be taken and frozen, to permit testing of total, WT and mutant TTR and other types of testing related to ATTR.

Details of how samples will be collected, processed, and stored will be in the Study Laboratory Manual. The Central Laboratory for TTR analysis is:

# 7.3.2 Transthyretin mRNA

Blood for serum TTR mRNA is to be collected at Screening, immediately prior (within 10 minutes) to the administration of the premedications on Days 0 (Baseline) and 28, and on Days 1, 2, 29, and 30. For optional cohorts dosed once every 3 weeks, blood for serum TTR mRNA will be collected at Screening and on Days 0 (Baseline) and 21, and on Days 1, 2, 22, and 23.

The Testing Laboratory for TTR mRNA analysis is:

### 7.3.2.1 Vitamin A and Retinol Binding Protein

Blood for measurements of vitamin A and RBP is to be collected at Screening, immediately prior (within 10 minutes) to the administration of the premedications, immediately pre-dose (within 10 minutes) on Days 0 and 28, and on Days 1, 2, 7, 10, 14, 21, 29, 30, 35, 38, 42, 49, 56 (end-of-study), 112, and 208 or at the time of early termination. For optional cohorts dosed once every 3 weeks, blood for measurements of vitamin A and RBP will be collected at Screening, immediately prior (within 10 minutes) to the administration of the premedications, immediately pre-dose (within 10 minutes) on Days 0 (Baseline) and 21, and on Days 1, 2, 7, 10, 14, 22, 23, 28, 31, 35, 42, 49, 56 (end-of-study), 112, and 208 or at the time of early termination.

Serum samples will be evaluated by HPLC to determine vitamin A levels and by nephelometry to determine RBP levels.

The laboratory for serum vitamin A and RBP analysis is:

### 7.4 Pharmacokinetic Evaluations

### 7.4.1 Plasma Pharmacokinetics

The PK parameter estimates and dose proportionality profiles of ALN-TTR02 will be determined for ALN-TTR02 siRNA (ALN-18328) and liposome lipid components, DLin-MC3-DMA and PEG2000-C-DMG. The plasma concentration-time profiles for ALN-18328, DLin-MC3-DMA, and PEG2000-C-DMG will be determined and used in the PK analysis for all dose cohorts. In addition, free and encapsulated concentrations of siRNA will be determined in plasma at specified time points (see Table 1-1) for cohort 3 and onward, including any optional cohorts. The drug concentrations in the lower cohorts are expected to be undetectable for this analysis.

Blood sample collection times are included in the schedule of events (see Table 1-1). Plasma PK samples (siRNA and lipids) will be collected pre-dose (within 1 hour of planned dosing start), at EOI, and then 5, 10, and 30 minutes, and at 1, 2, 4, 6, 24, and 48 hours post infusion. Samples will also be collected on Days 7, 14, 21, 35, 42, 49, 56, 112, and 208 post infusion as well as at the ET visit (if applicable); for optional cohorts

dosed once every 3 weeks, samples will be collected on Days 7, 14, 21, 28, 35, 42, 56, 112, and 208 post infusion as well as at the ET visit (if applicable).

For the PK blood draws, the sampling windows are  $\pm 1$  minute for the 5- and 10- minute draws;  $\pm 2$  minutes for the 30-minute draws;  $\pm 5$  minutes for the 1-, 2-, 4-, and 6-hour draws; and  $\pm 120$  minutes for the 24- and 48-hour draws.

The EOI will usually occur at 60 minutes after the start of infusion, except in patients where the infusion has been prolonged. If the infusion is stopped, a PK blood sample will be taken when the infusion is stopped, and this sample will be treated as the EOI sample if the infusion is restarted. All remaining PK samples will be collected according to the schedule of assessments when the dose is completed (i.e., all post-infusion times are relative to the EOI, regardless of the duration of infusion).

In the event that a patient receives only 1 dose of study drug, plasma PK samples should be collected pre-dose (within 1 hour of planned dosing start), EOI, and then 5, 10, and 30 minutes; and 1, 2, 4, 6, 24 and 48 hours post infusion; and at Day 208.

Details of sample collection and processing for PK analyses will be included in a laboratory manual.

Pharmacokinetic analyses will consist of a non-compartmental and/or compartmental evaluation of ALN-TTR02 siRNA (ALN-18328), and of ALN-TTR02 lipids DLin-MC3-DMA and PEG2000-C-DMG plasma concentration-time profiles to determine PK parameter estimates using a validated software program, Pharmacokinetic parameter estimates to be calculated for all patients receiving ALN-TTR02 will include, but may not be limited to:

- Observed Cmax.
- Time of observed maximum concentration  $(t_{max})$ .
- Partial area under the plasma concentration-time curve (AUCp).
- Area under the plasma concentration-time curve to the last measurable concentration (AUC $_{0-t}$ ).
- Area under the plasma concentration-time curve from zero to the last measurable time point (AUC0-last).
- Area under the plasma concentration-time curve extrapolated to infinity  $(AUC_{0-\infty})$ .

- Terminal elimination half-life  $(t_{1/2\beta}$  and  $t_{1/2\alpha})$ .
- Elimination rate constant  $(\lambda_z)$ .
- Systemic clearance (CL).
- Volume of distribution at steady state  $(V_{ss})$ .
- Volume of distribution based on the terminal phase (Vz).

Other parameters may be calculated if deemed necessary.

Plasma samples will be evaluated by using a validated ATTO-Probe-HPLC assay to determine ALN-18328 concentration. The concentrations of DLin-MC3-DMA and PEG2000-C-DMG in plasma samples will be evaluated by a validated liquid chromatography/mass spectrometry (LC/MS/MS) assay at

The Central Laboratory for plasma PK analysis is:

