#### 5.11 Suggested Guidelines for Management of Infusion Reactions

In the event of an acute infusion reaction, the infusion of study drug will be stopped and the patient closely monitored until resolution of the reaction. A blood sample should be obtained for analysis of tryptase, complement factors (including C3a), and cytokines at the time of the event, or as soon as possible after onset, 1 hour, and 24 hours after the start of the reaction. In addition, if the infusion is stopped and the site is considering restarting, a PK blood sample will be taken when the infusion is stopped and this will be treated as the EOI sample if the infusion is restarted.

Drugs that may be used to facilitate resolution and permit resumption of study drug administration include, but are not limited to: paracetamol (or equivalent), additional H1/H2 blockers (e.g., ranitidine), non-steroidal anti-inflammatory [NSAID], adrenaline, supplemental oxygen, IV fluids, and corticosteroids. For moderate infusion reactions (see Appendix 1), resumption of study drug administration at a slower infusion rate (but not to exceed 3 hours) may be considered at the Investigator's discretion. Study drug administration will not be resumed for any patient following a severe infusion reaction. If the infusion is delayed, the administration of the infusion should be completed no more than 6 hours from the initial start of the infusion.

Infusion reactions may have a delayed onset following the completion of the infusion. The medical management of a delayed reaction (e.g., use of corticosteroids, etc.) would follow similar guidelines as provided above for acute infusion reactions (see Appendix 2).

After dosing, patients will be discharged from the hospital no sooner than 24 hours post-dose. Prior to discharge, the 24-hour ECG and local serum chemistries and LFTs must be reviewed by the Investigator as described in Section 3.1. Patients will be discharged with directions on self-administration of medications as needed to ameliorate potential delayed reactions to study drug infusion, such as fever, chills, and myalgia. Medications may

include, but are not limited to: antipyretics, antihistamines, and oral corticosteroids. All concomitant medications, including self-administered medications, are to be listed on the CRF.

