#### 6.3.1.2 Administration of Study Drug

After completion of all pre-dose evaluations and procedures, administer study drug as a 60-minute IV infusion (or an approximate 70-minute IV infusion for patients in an optional cohort evaluating the alternative premedication regimen and infusion rate) via a controlled infusion device. Continue to assess the infusion site for signs of any localized reaction through 30 minutes post-infusion.

The infusion time may be extended up to 3 hours in the event of a mild or moderate infusion reaction (study drug administration will not be resumed for any patient following a severe infusion reaction). Suggested guidelines for treatment of infusion reactions are provided in Section 5.11. In addition, if the infusion is stopped and the site is considering restarting, a PK blood sample will be taken when the infusion was stopped. All remaining PK samples will be collected according to the schedule of assessments when the dose is completed.

Prior to administration of second dose of study drug, patients must be reassessed to confirm they continue to meet eligibility criteria.

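### The PK sample taken at an interruption is labelled end of infusion (EOI) when the infusion restarts, although the later samples are timed from the end of the completed dose

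*Protocol*

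**What the plan says.** **Relabelling.** Protocol 7.4.1 requires a PK sample when the infusion is stopped and adds that "this sample will be treated as the EOI sample if the infusion is restarted". Section 5.11 has the same rule: "this will be treated as the EOI sample if the infusion is restarted".

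**Later samples.** Section 7.4.1 continues: "All remaining PK samples will be collected according to the schedule of assessments when the dose is completed". It explains that "all post-infusion times are relative to the EOI, regardless of the duration of infusion".

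**Meaning of EOI elsewhere in 7.4.1.** "The EOI will usually occur at 60 minutes after the start of infusion", with an exception for prolonged infusions. Here EOI is the actual end of the infusion.

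**Parallel text.** Section 6.3.1.2 says, for a stop with a possible restart, that "a PK blood sample will be taken when the infusion was stopped". Neither it nor the synopsis calls this the EOI sample. Footnote z of Table 1-1 schedules an EOI sample for each dose.

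**How late the true end can be.** Section 5.11 provides for resumption at a slower rate and says that, after a delay, "the administration of the infusion should be completed no more than 6 hours from the initial start of the infusion".

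**Use of the EOI sample.** Footnote z has free and encapsulated siRNA measured on Day 0 at two times only, EOI and 2 hours after infusion, from cohort 3 onward. Section 7.4.1 also lists observed Cmax, tmax and several AUCs.

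**SAP.** Sections 1.1.2 and 4.4 leave PK to a separate analytical plan and report.

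**The concern.** If the infusion restarts, the interruption is by definition not its end. The sample drawn then reflects only the part of the dose given so far, and the rest follows after a pause. The rule is coherent only in the opposite case, when the infusion is not restarted. Whether a negation was lost cannot be told from the documents, but the wording stands in two sections and sites will follow it.

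Two things are at stake. One profile can combine an EOI value from the interruption with samples timed from dose completion. And since the EOI sample then counts as taken, a site may draw nothing at the true end and begin with the 5-minute sample. Restart is a foreseen pathway: Appendix 1 describes re-challenge, section 8.8 has a category for interruption and restart, and SAP 4.5.1 summarises interruptions. Plasma PK is a secondary objective, and a planned cohort has three patients.

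**Working it through.** The plan gives no figure to reproduce. The first step compares the text; the second sizes the possible error.

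**1. What EOI means, place by place**

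| Place | Meaning of EOI after a restart |
|---|---|
| 5.11 and 7.4.1, relabelling rule | the interruption |
| 7.4.1, usual time and prolonged infusions | the actual end of infusion |
| 7.4.1, timing of later samples | completion of the dose |
| 6.3.1.2 and synopsis | interruption sample required, not called EOI |
| Table 1-1, footnote z | one EOI sample for each dose |

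The relabelling rule is the odd one out. That no EOI sample is drawn at completion is an inference from the word *remaining* in 7.4.1; no section forbids the draw.

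**2. Size of the labelling error (illustrative)**

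From the documents: 60-minute planned infusion, slower rate on restart, completion within 6 hours of the start. Assumed: one compartment, half-life 0.5, 1, 2 or 6 h, stop at a fraction *f* = 0.25, 0.50 or 0.75 of the dose, 30-minute pause, restart at the same rate or at one third of it (an arbitrary choice of slower rate).

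With unit dose and volume, k = ln 2 / half-life, R1 = 1/60 per minute, t1 = 60*f*, and t2 = 60(1 − *f*) at the same rate or 180(1 − *f*) at one third:

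- C(stop) = (R1/k)(1 − e^(−k·t1))
- C(true EOI) = C(stop)·e^(−k(30 + t2)) + (R2/k)(1 − e^(−k·t2))

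Example, *f* = 0.50 and half-life 30 minutes:

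- C(stop) = 0.361.
- Same rate, end at 90 minutes: 0.361 × 0.25 + 0.361 = 0.451; ratio 0.361/0.451 = 0.80.
- One third of the rate, end at 150 minutes: 0.361 × 0.0625 + 0.240 × 0.875 = 0.233; ratio 0.361/0.233 = 1.55.

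Range of C(stop)/C(true EOI) over the four half-lives:

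| Stopped at | Same rate | One third of the rate |
|---|---|---|
| 25% of dose | 0.26–0.42 | 0.29–0.90 |
| 50% | 0.53–0.80 | 0.58–1.55 |
| 75% | 0.79–1.24 | 0.83–1.96 |

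The ratio falls on both sides of 1, so no fixed correction factor would repair the value.

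**3. What the other samples protect**

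The 5-minute sample is e^(−5k) of the true EOI concentration: 0.89 at a half-life of 0.5 h, 0.94 at 1 h and 0.99 at 6 h. It limits the loss for Cmax.

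For AUC, a wider set of scenarios was run: stop at 15 to 45 minutes, pause 30 to 180 minutes, remainder over 15 to 150 minutes. With half-lives of 4 h and 24 h, the trapezoidal AUC to 6 hours after EOI, relative to the model value, was:

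- interruption value placed at the true EOI time: 0.78–0.95;
- interruption value at its actual time, no EOI sample: 1.01–1.15;
- both samples at their actual times: 1.01–1.16.

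At these half-lives actual timing alone removes nearly all of the labelling error in AUC. At a 15-minute half-life, sparse sampling during infusion adds error even with correct labels.

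Neither step helps the free and encapsulated siRNA reading: no 5-minute sample is scheduled for that assay. The model describes a single concentration and says nothing about the split between free and encapsulated siRNA.

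**The case against.** The strongest reply is that this is a wording conflict with limited consequences. Much of that stands.

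- **A reader might infer that no true EOI sample will exist.** The documents do not say so. Footnote z schedules one for each dose, and 6.3.1.2 can be read as allowing it at completion.
- **A reader might infer that Cmax, tmax and AUC will be wrong.** That depends on the separate PK plan. With actual times, the interruption sample is a valid mid-infusion concentration. If it exceeds every later value, it is still a concentration genuinely observed.
- **A reader might infer that the EOI value will always be too low.** With a slower restart it can be too low, about right or too high.
- **A reader might infer that all patients with infusion reactions are affected.** Severe reactions are not restarted, and delayed reactions begin after the infusion is complete.
- **A reader might infer that a planned exposure–reaction analysis is compromised.** None is planned. Protocol 9.2.6 relates exposure to TTR, and the SAP tabulates and lists infusion reactions.
- **One patient is not always a third of the group.** SAP 3.5 pools cohorts with the same dose and regimen.

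What the reply does not answer is that the rule in 5.11 and 7.4.1, applied literally, attaches the EOI label to a mid-infusion sample. Actual times can correct a timestamp; they cannot supply a sample that was not drawn.

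**Conclusion.** The relabelling rule is wrong as written and conflicts with the rest of 7.4.1; 6.3.1.2 and the synopsis do not carry it. In an interrupted and restarted infusion it records a mid-infusion concentration as EOI and may leave no sample at the true end.

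The firmest consequence is for the Day 0 free and encapsulated siRNA reading from cohort 3 onward, where EOI is one of only two time points. Effects on Cmax, tmax and AUC are possible, not established. Under the stated assumptions the recorded EOI value would be about 0.26 to 1.24 times the true one at the same restart rate, and 0.29 to 1.96 times at one third of the rate. Half-lives, stop points, pause and restart rate are assumptions.

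The point should be corrected. It touches a secondary objective and few patients, and the primary safety analysis does not depend on it.

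**What to change.** In 5.11 and 7.4.1:

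- Record the interruption sample under its own label with its actual time.
- Draw the EOI sample that footnote z already schedules at the end of the completed infusion.
- Treat the interruption sample as EOI only when the infusion is not restarted.

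Align 6.3.1.2 with this wording, and have the separate PK plan state that actual elapsed times are used. For the Day 0 free and encapsulated siRNA assay, specify the sample at the end of the completed infusion.

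The cost is one additional blood draw per restarted infusion, plus wording. The change concerns PK sampling and labelling only, not how infusions are managed.
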